8.2.3 Premature Subject Withdrawal

In accordance with the Declaration of Helsinki (48th WMA General Assembly, Somerset West, Republic of South Africa, October 1996), subjects have the right to withdraw participation from the study at any time for any reason. Every reasonable attempt should be made by the investigator to keep subjects in the study; however, subjects must be withdrawn from the study if they withdraw consent to participate. Investigators must make at least 3 attempts to contact subjects who fail to attend scheduled visits by telephone or any other means.

The investigator also has the right to remove subjects from the study for the following reasons:

- Adverse events: If the reason for removal of a subject from the study is an AE, the principal specific event and any related test results will be recorded on the electronic case report form (eCRF). If a subject withdraws because of an AE plus another reason, the withdrawal will be considered due to the AE and the eCRF will be completed to reflect this reason for withdrawal. A narrative description will be required for all early withdrawals due to AEs.
- The request of the subject, his/her representative, investigator or sponsor, whether for administrative or other reasons.
- Noncompliance with study drug or non-compliance with subject eDiary completion, protocol violation, or unreliable behavior.
- Pregnancy. If the subject becomes pregnant during the clinical study, the study drug should be stopped immediately and the subject will be withdrawn from the study and followed until delivery.

If a subject is withdrawn early from the study, the following procedures will be performed:

- The date of the last dose of study drug and all observations collected up to the time of termination will be recorded on the Early Withdrawal eCRF page along with the reason for termination. All Early Withdrawal procedures should be completed and recorded on the Early Withdrawal eCRF page. If withdrawal occurs at a regular scheduled visit, the

Early Withdrawal eCRF page should be used instead of the regular visit eCRF page to record any information related to the visit.

- In order to enable the most complete recording of any subject who withdraws early from the study, it is important to evaluate these subjects at the study center as soon as possible. Subjects who are withdrawing early should undergo an Early Withdrawal/Termination Visit and a Follow-up Safety Visit must be scheduled.

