10.1.4 Follow-up Visit

A follow-up phone Visit will take place approximately 7 days after the end-of-treatment (EOT) visit (or Early Termination Visit), and will include the following assessment and procedures:

1. Review subject's use of concomitant medications.
2. Review AEs.

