11.2. Management of Adverse Events

Adverse events will be collected from the time of first dose administration through the Follow-up Visit or Early Termination Visit, whichever occurs first.

Subjects who complete the Double-blind Treatment Phase or terminate early will continue to be monitored for AEs for 30 days from last day for study treatment, unless they withdraw consent or are lost to follow-up.

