13.4.4.1 Adverse Events

All AEs will be coded using Medical Dictionary for Regulatory Activities (MedDRA), **Version 19**.

Treatment-emergent AEs are defined as:

- AEs with onset at the time of or following the start of treatment with study drug through the Follow-up Visit or Early Termination Visit, whichever occurs first. The number and percentage of subjects with AEs will be displayed for each treatment group by system organ class and preferred term. Summaries of AEs by severity and relationship to study drug will also be provided. Serious adverse events and AEs resulting in discontinuation

of study drug will be summarized separately in a similar manner. Subject listings of AEs, SAEs, and AEs causing discontinuation of study drug will be produced.

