8.1. Adverse Events

All adverse events collected are treatment-emergent adverse events (TEAEs) since only AEs after treatment start are collected. All AEs, and SAEs will be coded using the MedDRA version 19.0 thesaurus.

The frequency and percentage of subjects reporting AEs, grouped by MedDRA system organ class and preferred term, will be tabulated by severity and treatment group for the SAF. Such summaries will be displayed for AEs, SAEs, AEs by relationship to study drug, and AEs by severity.

In the case of multiple occurrences of the same AE within the same subject, each subject will only be counted once for each preferred term. In the summaries showing severity and relationship to study medication the event with the maximum severity or strongest relationship will be reported. If a particular event is missing the severity and/or relationship, then the strongest possible severity or relationship will be assumed for analysis (severity = severe, relationship = definitely related).

Missing and partially missing AE start and/or stop dates will be imputed for the purpose of statistical analysis, according to the specifications described in Section [5.1.8](#).

In the AE data listings, all AEs will be displayed.

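### The stated end of adverse event collection gives early terminators a shorter window for new non-serious events than completers, conflicts with other protocol text, and leaves the SAP's safety tables without a defined window

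*Protocol*

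**What the plan says.** All references are to the current protocol (Amendment 2) and the SAP.

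- **Collection rule, Protocol 11.2:** collection starts at the first dose and runs "through the Follow-up Visit or Early Termination Visit, whichever occurs first".
- **Next paragraph of 11.2:** subjects who complete, and those who stop early, "will continue to be monitored for AEs for 30 days from last day for study treatment".
- **Treatment-emergent definition, Protocol 13.4.4.1:** "AEs with onset at the time of or following the start of treatment with study drug through the Follow-up Visit or Early Termination Visit", again taking the earlier of the two.
- **Follow-up contact, Protocol 10.1.4:** "A follow-up phone Visit will take place approximately 7 days after the end-of-treatment (EOT) visit (or Early Termination Visit"). Adverse events are reviewed at that contact.
- **Early withdrawal, Protocol 8.2.3:** besides the withdrawal visit, "a Follow-up Safety Visit must be scheduled".
- **Overall design, Protocol 7.1:** adverse events are documented from study drug administration up to the post-treatment visit.
- **Documentation, Protocol 11.2.3:** events within the period of observation go on the eCRF, and the reader is sent to 11.2 for that period.
- **Ongoing events, Protocol 11.2.5:** non-serious events ongoing at discontinuation are followed for up to 7 days.
- **Serious events, Protocol 11.2.6.1:** collected through the Termination Visit and for 30 days after discontinuation, whichever is longer.
- **SAP 8.1:** "All adverse events collected are treatment-emergent adverse events (TEAEs) since only AEs after treatment start are collected". No end of window is given. SAP Section 9 reports no changes from the planned analysis.

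**The concern.** A completer has no ET visit, so the window closes at the follow-up contact. For a subject who attends an ET visit, that visit always precedes the follow-up contact and closes the window. The protocol thus orders an adverse event review after the ET visit and, in 11.2, ends collection before the review takes place. Because 11.2.3 defers to 11.2, the conflict decides what reaches the database: a site applying the first sentence of 11.2 need not enter a new non-serious event reported at the post-ET call, and a site applying the second would enter it.

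At stake is like-for-like ascertainment. Protocol 7.1 withdraws subjects who cannot tolerate their dose, so early terminators include people who matter for tolerability. Safety and tolerability is a secondary objective, and SAP 2.1.2 frames it as a comparison with placebo. If early termination differs between arms, so would the length of observation behind the event counts.

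**Working it through.** **The plan's own figure.** The synopsis puts end of treatment at Day 28 and follow-up at Day 35: 35 − 28 = 7 days, which matches Protocol 10.1.4 and the one week after last dose in Protocol 7.2. If the ±2-day windows apply to both nominal days, the interval runs from (35 − 2) − (28 + 2) = 3 to (35 + 2) − (28 − 2) = 11 days.

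**Post-treatment window, read literally.** Let L be the days from last patch to ET visit. Protocol 8.2.3 asks for that evaluation as soon as possible but gives no number, so L = 0 to 7 is an assumption.

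- Completer: 7 days.
- Early terminator: L days.
- Difference: 7 − L days.
- Shortfall against the 30-day sentence: 30 − 7 = 23 days for a completer, 30 − L for an early terminator.

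**If collection ran through the follow-up contact for everyone.** That contact is timed from the ET visit, so an early terminator would have L + 7 days after last patch, against 7 for a completer.

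| L (assumed) | Early terminator, literal | Gap to completer (7 − L) | Short of 30 days (30 − L) | Through follow-up contact (L + 7) |
|---|---|---|---|---|
| 0 | 0 | 7 | 30 | 7 |
| 1 | 1 | 6 | 29 | 8 |
| 3 | 3 | 4 | 27 | 10 |
| 7 | 7 | 0 | 23 | 14 |

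Two things follow. The literal rule is unequal unless L happens to be 7. And extending collection to the follow-up contact does not by itself give equal windows, because L + 7 exceeds 7 whenever L is above 0; the analysis window has to be counted in days from last patch.

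**What each provision covers for an event starting after the ET visit.**

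| Event | Protocol 11.2, first sentence | Other protocol text | Treatment-emergent, Protocol 13.4.4.1 | Treatment-emergent, SAP 8.1 |
|---|---|---|---|---|
| New non-serious | Not collected | Reviewed at the call (10.1.4); monitored for 30 days (11.2) | No | Yes, if recorded |
| New serious, within 30 days | Not collected | Collected (11.2.6.1) | No | Yes, if recorded |

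The two documents classify the same recorded event differently.

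**The case against.** The strongest reply is that the short window is one sentence against several. The 30-day sentence, the call after the ET visit, the compulsory Follow-up Safety Visit and the documentation period in 7.1 all point to follow-up after early termination, so sites may well have recorded these events. SAP 8.1 truncates nothing itself: an event entered from the call would be tabulated. Safety is a secondary objective, with no formal inference planned unless otherwise noted.

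Much of this stands. It makes the defect an unresolved recording rule rather than a demonstrated loss of data. It does not remove the defect, because 11.2.3 points to 11.2 for what must be recorded and the SAP can count only what was entered.

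A reader might infer more than the documents support:

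- **That serious or delayed systemic events go uncollected after early termination.** Protocol 11.2.6.1 collects serious events for 30 days, and drug-related ones are reportable without time limit. What is exposed is new-onset non-serious events, plus the treatment-emergent label for late serious ones.
- **That early terminators get no post-treatment observation.** That holds only if the ET visit falls on the day of the last patch (L = 0). Non-serious events already ongoing at discontinuation are in any case followed for up to 7 days.
- **That a known share of subjects is affected, or that the arms are biased by a known amount.** The documents give no early-termination rate, no split of withdrawal reasons and no post-discontinuation event rate.

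**Conclusion.** The point holds in a limited form. Protocol 11.2 and 13.4.4.1, read as written, close the window for new non-serious events at the ET visit for early terminators and at about 7 days after treatment for completers. The difference is 7 − L days: 7 if the ET visit is on the last-patch day, 0 if it is 7 days later. Under 13.4.4.1, a serious event starting after the ET visit is collected but is not treatment-emergent.

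The rule contradicts 7.1, 8.2.3, 10.1.4 and the second paragraph of 11.2. Completers are affected by that last conflict too, since their window is 23 days short of the 30-day statement. Which window governs the safety tables is unresolved, because SAP 8.1 sets none.

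The conclusion assumes the literal reading of 11.2 and a subject who attends an ET visit. The direction of any error is under-counting of late non-serious events in early terminators; its size cannot be calculated. The primary efficacy analysis is untouched. It should be corrected, since the contradiction is plain and the remedy is cheap.

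**What to change.** 1. In Protocol 11.2 and 13.4.4.1, remove the ET visit as an alternative end point together with the earlier-of clause, so that collection of non-serious events runs through the follow-up contact that 10.1.4 already schedules for both groups.
2. Define the treatment-emergent window as one stated number of days after last patch, the same for completers and early terminators, ending no later than that contact. The length is the sponsor's choice. Since stacked visit windows could bring the contact as early as 3 days after the end-of-treatment visit, the call should not be placed before the chosen window closes.
3. Use the same window in SAP 8.1, and state there how serious events with later onset are reported.
4. Reconcile the result with the 30-day sentence in 11.2, the 7-day follow-up of ongoing events in 11.2.5 and the serious event rule in 11.2.6.1.

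If the window ends by the scheduled call, the cost is wording. If the sponsor keeps 30 days for non-serious events, a further contact has to be added, because no routine contact is scheduled after the follow-up call.

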11.2.1 Collection

The investigator is responsible for the detection and documentation of events meeting the criteria and definition of an AE or SAE described previously. At each visit, the subject will be allowed time to spontaneously report any issues since the last visit or evaluation. The investigator will then monitor and/or ask about or evaluate AEs using non-leading questions, such as:

- “How are you feeling?”
- “Have you experienced any issues since your last visit?”
- “Have you taken any new medications since your last visit?”

11.2.2 Any clinically relevant observations made during the visit will also be considered AEs. Evaluation

11.2.2.1 Severity of Adverse Events

The clinical severity of an AE will be classified as

Mild	Usually transient and may require only minimal treatment or therapeutic intervention. The event does not generally interfere with usual activities of daily living.
Moderate	Usually alleviated with additional specific therapeutic intervention. The event

	interferes with usual activities of daily living, causing discomfort but poses no significant or permanent risk of harm to the subject.
Severe	Interrupts usual activities of daily living, or significantly affects clinical status, or may require intensive therapeutic intervention.

It is important to distinguish between severe AEs and SAEs. Severity is a classification of intensity whereas an SAE is an AE that meets serious criteria, as described in [Section 11.1.3](#).

11.2.2.2 Seriousness

The investigator is to evaluate whether the AE meets serious criteria, as described in [Section 11.1.3](#).

11.2.2.3 Action Taken

Action taken may consist of:

Drug withdrawn	An indication that a medication schedule was modified through termination of a prescribed regimen of medication.
Not applicable	Determination of a value is not relevant in the current context.
Unknown	Not known, not observed, not recorded, or refused.

11.2.2.4 Outcome at the Time of Last Observation

The outcome at the time of last observation will be classified as follows:

- Recovered/resolved
- Recovered/resolved with sequelae
- Recovering/resolving
- Not recovered/not resolved
- Fatal*
- Unknown

NOTE: Only select fatal as an outcome when the AE results in death. If more than 1 AE is possibly related to the subject's death, the outcome of death should be indicated for each such AE. Although "fatal" is usually an event outcome, events such as sudden death or unexplained death should be reported as SAEs.

11.2.2.5 Adverse Event Relationship to Investigational Product

The investigator must make an assessment of each AE's relationship to study drug. The categories for classifying the investigator's opinion of the relationship are listed below.

Not related	An AE with sufficient evidence to accept that there is no causal relationship to study drug administration (e.g., no temporal relationship to drug administration, because the drug was administered after onset of event; investigation shows that the drug was not administered; another cause was proven).
Unlikely related	An AE, including laboratory test abnormality, with a temporal relationship to study drug administration that makes a causal relationship improbable, and in which other drugs, events or underlying disease provide plausible explanations.
Possibly related	An AE with a reasonable time sequence to administration of the study drug, but which could also be explained by concurrent disease or other drugs or events. Information on drug withdrawal may be lacking or unclear.
Definitely Related	An AE occurring in a plausible time relationship to study drug administration, and which cannot be explained by a concurrent disease or other drugs or events. The response to withdrawal of the drug (dechallenge) is clinically reasonable.

11.2.3 Documentation

All AEs occurring within the period of observation for the study must be documented in the eCRF with the following information; where appropriate (The period of observation for the study is described in **Section 11.2**):

- AE name or term
- When the AE first occurred (start date and time)
- When the AE stopped (stop date and time or an indication of “ongoing”)
- Severity of the AE
- Seriousness (hospitalization, death, etc.)
- Actions taken
- Outcome
- Investigator opinion regarding the AE relationship to study drug

11.2.4 Treatment of Adverse Events

Adverse events that occur during the study will be treated, if necessary, by established standards of care. If such treatment constitutes a deviation from the protocol, the subject should be withdrawn from the study and the reason and date of withdrawal must be documented in the eCRF. The decision about whether the subject may continue in the study will be made by the sponsor after consultation with the investigator and/or medical monitor.

If AEs occur in a subject that is not tolerable, the investigator must decide whether to withdraw the subject from the study and/or treat the subject. Special procedures may be recommended for the specific study drug, such as the collection of a serum sample for determining blood concentrations of study drug, or treatment regimens, as appropriate.

It is **NOT** necessary to unblind a subject's treatment assignment in most circumstances, even if an SAE has occurred. If unblinding is necessary, see **Section 9.5** for a description of the unblinding procedures.

11.2.5 Follow-up

ALL ongoing SAEs at the time of discontinuation will be followed (up to a maximum of 30 days after the last dose of study medication) to a satisfactory resolution, or until it becomes stable, or until it can be explained by another known causes (i.e., concurrent condition or medication) and clinical judgment indicates that further evaluation is not warranted. All ongoing AEs at the time of discontinuation will be followed for up to 7 days. All findings relevant to the final outcome of an AE must be reported in the subject's medical record and recorded on the eCRF page.

11.2.6 Reporting of Adverse Events

11.2.6.1 Serious Adverse Events

The investigator or designee must report all SAEs promptly to [REDACTED] within 24 hours of first becoming aware of the event by completing, signing and dating the Serious Adverse Event Report Form, verifying the accuracy of the information recorded in the form with the source documents and eCRF, and sending the SAE form to the sponsor by one of the following methods:

All SAEs, irrespective of relationship to study treatment, must be reported as soon as possible but no later than 1 business day by Fax to:

Email: [REDACTED]
[REDACTED]

The “Clinical Trial Serious Adverse Event Report Form (SAE form)” must be used for reporting.

It is very important that the SAE report form be filled out as completely as possible at the time of the initial report. This includes the investigator's assessment of causality. All SAEs must be followed to resolution, or if resolution is unlikely, to stabilization. Any follow-up information

received on serious adverse events should be forwarded within one business day of its receipt. If the follow-up information changes the investigator's assessment of causality, this should also be noted on the follow-up SAE form.

SAEs, regardless of causality assessment, must be collected through the Termination Visit and for 30 days following study drug discontinuation, whichever is longer.

Any SAE judged by the investigator to be related to the study treatment should be reported to the sponsor regardless of the length of time that has passed since study completion.

The written report should be submitted on the SAE form provided for this purpose. At the time of first notification, the investigator or designee should provide the following information, if available:

- Protocol number
- Reporter (study site and investigator)
- Subject's study number
- Subject's year of birth
- Subject's gender
- Date of first dose of study drug
- Date of last dose of study drug, if applicable
- Adverse event term
- Date of occurrence of the event
- A brief description of the event, outcome to date, and any actions taken
- The seriousness criteria that were met
- Concomitant medication at onset of the event
- Relevant medical history information
- Relevant laboratory test findings
- Investigator's opinion of the relationship to study drug ("Is there a reasonable possibility that the study drug caused the SAE? Yes or No?")
- Whether and when the investigator was unblinded as to the subject's treatment assignment

The investigator must fax/mail a written SAE Report Form that describes the SAE to the recipients of the initial information, who will forward the information to the sponsor.

Preliminary SAE reports and/or any missing or additional relevant information concerning the SAE should be provided to the recipients of the initial information as soon as possible on a follow-up SAE Report Form, together with the following information (adverse event, date of occurrence, subject ID, study ID, study drug, and site number) including copies of hospital case reports, autopsy reports and other documents requested by the sponsor; this will allow the follow-up information to be linked to the initial SAE report.

The investigator is required to comply with applicable regulations (including local laws and guidances) regarding the notification of his/her health authorities, institutional review board (IRB), principal and coordinating investigators, study investigators, and institutions.

11.2.6.2 Nonserious Adverse Events

Nonserious AEs will be recorded in the eCRF page and reported by [REDACTED] to Noven.

11.2.7 Adverse Events of Special Interest

The overall systemic safety profile of diclofenac is well known and established as reflected in the Investigator's Brochure (IB) including Developmental Core Safety Information, which are in part based on the current label of the [REDACTED] In patients taking [REDACTED]

[REDACTED]
[REDACTED]
[REDACTED]
[REDACTED]
[REDACTED]
[REDACTED]

The overall safety of HP-5000 patches at doses ranging from [REDACTED]

[REDACTED]
[REDACTED]

[REDACTED] The HP-5000 patches used in the clinical studies [REDACTED]

[REDACTED] Some of the commonly reported AEs across the [REDACTED]

[REDACTED] The remaining commonly reported AEs are either known adverse reactions to other commercially available dose forms that contain diclofenac (application site pruritus, back pain, and myalgia with diclofenac containing solutions or patches) or consistent with events of application site skin reactions commonly reported as AEs

with other topical medications that contain diclofenac [REDACTED]
[REDACTED]

